SPGT Serum Glutamic Pyruvic Transaminase

WBC White Blood Cells

STUDY SCHEMA

STUDY SUMMARY

Title	The Role of 5-Aminolevulinic Acid Fluorescence-Guided Surgery in Head and Neck Cancers: a Pilot Trial
Short Title	5-ALA FGS Pilot Trial for Head and Neck Cancer
Protocol Number	The standard protocol number used to identify this study- N/A
Methodology	Open label single institution pilot study
Study Duration	2 ^{1/} ₂ years
Study Center(s)	Single center
Objectives	The objectives of this study are to determine the feasibility of using 5-ALA in fluorescence-guided surgery of head and neck and skull base malignancies.
Number of Subjects	23
Diagnosis and Main Inclusion Criteria	 Resectable head and neck or skull base malignancy Age 18-80 Karnofsky score >60%, adequate marrow and organ function Not pregnant Able to give consent
Study Product(s), Dose, Route, Regimen	Single dose administration of oral Gleolan® (5-ALA) (20mg/kg) 3-5h prior to surgery
Duration of administration	Day of surgery
Reference therapy	N/A
Statistical Methodology	Assuming a prevalence of 75% and a sample sensitivity of 85%, the

sample size needed to estimate a two-sided 95% sensitivity confidence interval with a width of at most 35% (± 17.5% precision assuming asymptotic with continuity correction method) is at least 23). The sample size calculation is performed conservatively assuming only 1 measure per patient, but there will be typically 4 per patient which will improve precision of estimates.

We expect to enroll the necessary patients in 6 months at a rate of approximately 4 patients per month. This accrual rate is based on historical monthly rates of surgery in this patient population at the Mount Sinai hospital.

Analysis of the primary endpoint

To assess the performance of 5-ALA as a feasible method to detect tumor tissues, the point estimate of sensitivity will be computed according to the following definition:

Sensitivity: proportion of tumor tissues that tested positive on 5-ALA induced fluorescence.

The definition of a positive test is the fluorescence score equal to or greater than 1. For the assessment of sensitivity and specificity, histological diagnoses of any upper aerodigestive head and neck cancer in addition to squamous cell carcinoma, carcinoma in situ, and severe and moderate dysplasia were classified as malignant, whereas light dysplasia and normal tissue will be classified as benign by pathologists. Each patient is expected to contribute multiple samples and the pathologists will determine presence of malignancy in each sample. A contiguous table (fluorescence scores vs. pathological results) that presents the frequency and percentage of each cell will be prepared. A generalized estimating equation (GEE) model accounting for repeated measure within each patient will be used to estimate the sensitivity, specificity, PPV, and NPV. For sensitivity and specificity, the dependent variable is the PPIX fluorescence test result (positive vs. negative) and the independent variable is presence of tumor cells (tumor vs. normal).

Analysis of the secondary endpoints

For specificity, the point estimate will be computed according to the following definition:

Specificity: proportion of normal tissues that tested negative on 5-ALA induced fluorescence.

The definition of a negative test is a fluorescence score of 0. For sensitivity and specificity, the dependent variable is the PPIX fluorescence test result (positive vs. negative) and the independent variable is presence of tumor cells (tumor vs. normal).

For PPV and NPV, the dependent variable is presence of tumor and the independent variable is the test result. The point estimate along with a corresponding two-sided 95% confidence interval will be provided using PROC GENMOD.

The 5-ALA related adverse events will be recorded using standardized toxicity criteria and known side effect profile. Frequency of each observed adverse event will be calculated at each monitor time point. The rate of each adverse effect will be estimated as the number of adverse events within 6 weeks after surgery divided by the number of person days followed. The point estimate of the incidence rate along with a corresponding two-sided 95% confidence interval will be provided using PROC GENMOD. A generalized estimating equation (GEE) model accounting for repeated measure within each patient will be used to estimate the sensitivity, specificity, PPV, and NPV.

1.0 BACKGROUND AND RATIONALE

1.1 Background

5-ALA has been used in the treatment of malignant gliomas in neurosurgical interventions. FGS permits the intraoperative visualization of malignant tissue in real time guidance for differentiating tumor from normal brain tissue that is independent of neuronavigation. Tissue fluorescence after oral administration of 5-ALA has high sensitivity, specificity, and positive predictive values for identifying malignant glioma tumor tissue. 5-ALA-induced tumor fluorescence in diffusely infiltrating gliomas with non-significant magnetic resonance imaging contrast-enhancement permits intraoperative identification of anaplastic foci and establishment of an accurate histopathological diagnosis for proper adjuvant treatment. We conducted an extensive literature review and noted no current applications to sinonasal skull base tumors or head and neck tumors.

5-ALA is a hemoglobin metabolic pathway metabolite that can be orally administered. It accumulates within tumor tissue and surrounding infiltrative cancer cells and is metabolized into protoporphyrin IX (PpIX), a fluorescent metabolite that that can be visualized after activation with 405nm blue light. As factors associated with 5-ALA fluorescence include cellular density, tumor cell proliferative activity, and neovascularization, elevated PpIX production and tissue fluorescence is a highly sensitive, specific, and positive predictor marker for malignant tumor tissue.³ While other fluorescent markers such as fluorescein sodium have been demonstrated to be efficacious for FGS as well, one study found 5-ALA to be better for detecting tumor cells,⁴ and another found it more cost-effective.⁵ Therefore 5-ALA was chosen as the target of this investigation.

The utility of intraoperative 5-ALA has been demonstrated through its development for neurosurgical resection of glioma,⁵⁻¹⁴ glioblastoma multiforme,^{15,16} medulloblastoma,¹⁷ meningioma and other intracranial tumors,¹² as well as spinal tumors.¹⁸ It has been shown to be safe for intraoperative use,¹⁹ to increase gross total resection rates,⁵ and to yield high positive predictive value for tumor tissue.²⁰ Similarly, 5-ALA has been shown to be more sensitive than contrast MRI or PET scan in glioblastoma resection,^{20,21} and to yield a synergistic effect in improving glioma resection outcomes when combined with intraoperative MRI.²²

In recent years, many surgical subspecialties have increasingly recognized the utility of 5-ALA at accurately visualizing precancerous and cancerous tissue. Its use has expanded to photodynamic diagnosis and phototherapy of urothelial, ²³ gastric, ²⁴ prostate, ²⁵ and ovarian cancers. ²⁶ In particular, 5-ALA has also shown utility in identifying oral cancers, ²⁷ and in endoscopic identification of laryngeal malignancies in conjunction with autofluorescence bronchoscopy. ²⁸⁻³² Similarly, trials with autofluorescence have successfully demonstrated the effectiveness of fluorescence-based technologies at improving head and neck cancer detection and increasing successful surgical margins of oral squamous cell carcinoma excision. ^{33,34} While 5-ALA FGS and other fluorescence-based techniques appear promising for potential use in head and neck malignancies, ³⁵ no clinical trials have yet assessed intraoperative use of 5-ALA for improving resection of head and neck cancers and skull base tumors.

1.2 Study Agent(s) Background and Associated Known Toxicities

1.2 5-Aminolevulinic Acid

5-ALA is a naturally occurring substance that is found in all organisms, including humans, and is a necessary part of many basic metabolic life processes.

5-Aminolevulinic Acid HCI

C5H9NO3 MW 167.6

$$H_2N$$
 OH

Approximately 350 mg of 5-ALA is synthesized in humans each day for heme production. Administration of exogenous 5-ALA, results in the production of high intracellular (mitochondrial) concentrations of (PPIX). 5-ALA and PPIX (and other porphyrins) are respectively excreted in the urine and the stool.

1.2.1 Pharmacology

Aminolevulinic acid (ALA) is the first step in the biochemical synthesis of hemoglobin in animals. Aminolevulinic acid is a metabolic precursor of protoporphyrin IX (PPIX), which is a photosensitizer. The metabolism of 5-ALA is normally tightly controlled by feedback inhibition reflecting likely the intracellular levels of hemoglobin. The feedback control is through the enzyme, 5-ALA synthetase. Exogenous oral 5-ALA, bypasses this feedback inhibition and PPIX accumulates to be converted into heme. Excess 5-ALA and PPIX are thus excreted.

1.2.2 Pharmacokinetics

General characteristics

5-ALA is soluble in water and well absorbed through the GI tract. After ingestion, 5-ALA dosing at 20mg/kg, is metabolized to fluorescent porphyrins, predominantly protoporphyrin IX (PPIX).

Absorption

5-ALA HCl as an oral solution is rapidly and completely absorbed and peak plasma levels of 5-ALA are reached 0.5-2 hours after oral administration of 20 mg/kg body weight. With a terminal half-life of 45 minutes, plasma levels return to baseline values 24 hours after administration of an oral dose of 20 mg/kg/ body weight. 5-ALA is generally given on an empty stomach prior to induction of anesthesia.

Distribution and Biotransformation

Oral 5-ALA is metabolized by the liver, kidney, endothelial cells, skin, as well as by malignant gliomas (WHO grade III and IV) and metabolized to fluorescent PPIX. The plasma protein binding of 5-ALA is 12%. Four hours after oral administration of 20 mg/kg/body weight 5-ALA HCI, the maximum PPIX plasma level is reached. PPIX plasma levels rapidly decline and are not detectable 48 hours after administration. In a human pharmacokinetic study (N= 6) using a 128 mg dose of sterile intravenous 5-ALA HCI and oral 5-ALA HCI (equivalent to 100 mg 5-ALA) in which plasma 5-ALA and PPIX were measured, the mean half-life of 5-ALA was 0.70 \pm 0.18 h after the oral dose and 0.83 \pm 0.05 h after the intravenous dose. The oral bioavailability of 5- ALA was 50-60% with a mean Cmax of 4.65 \pm 0.94 μ g/mL. PPIX concentrations were low and were detectable only in 42% of the plasma samples. PPIX concentrations in plasma were quite low relative to 5-ALA plasma concentrations, and were below the level of detection (10 ng/mL) after 10 to 12 hours.

At the oral 5-ALA dose of 20 mg/kg/body weight, tumor:normal brain fluorescence ratios are usually high and provide for 'blue light' visualization of fluorescent tumor tissue as red-violet for at least 9 hours. Besides tumor tissue, faint fluorescence of the choroid plexus has been reported. 5-ALA is also taken up and metabolized to PPIX by other tissues, e.g. liver, kidneys or skin (see section 4.4).

Elimination

[figure not shown]
5-ALA is eliminated quickly. Approximately 30% of an orally administered dose of 20 mg/kg/body weight is excreted unchanged in urine within 12 hours.

Linearity/non-linearity

There is dose proportionality between AUC0-inf. of 5-ALA values and different oral doses of this medicinal product. The oral dose (20mg/kg body weight) provides an AUC (mg x h/L) of 26.91 (mean) and 27.14 (median).

Patients with renal or hepatic impairment

The pharmacokinetics of 5-ALA in patients with renal or liver impairment has not been investigated. Renal toxicity of the material has been described in association with acute intermittent porphyria and lead exposure.

1.2.3 Toxicity

In vivo toxicological effects associated with elevated levels of 5-ALA, PPIX, and intermediates of porphyrin biosynthesis are well known. These characterize metabolic diseases known as porphyrias. High systemic concentrations of 5-ALA are associated with neurological abnormalities in Acute Intermittent Porphyria (AIP). The relationship is not well understood. 5- ALA and Porphobilinogen (PBG = condensation of 2 molecules of 5-ALA) are not neurotoxic when administered in large amounts to animals and humans. In porphyric patients, the resulting brain or spinal fluid concentration of these precursors is below that required to cause toxicity using in vitro models. It is thought that patients with AIP have depletion of hepatic heme and neurologic symptoms related to elevated brain concentrations of tryptophan and 5- hydroxytryptamine. Thus oral 5-ALA would not deplete hepatic heme, and would not be expected to produce neurological symptoms of AIP. Erythropoietic Protoporphyria (EPP) with reduced conversion of PPIX to heme is associated with photosensitivity, reflecting high systemic and skin levels of PPIX. Patients with EPP experience no hemolytic or neurological problems.

Side effects of 5-ALA administration are uncommon (>=1/1000, <1/100) and include hypotension, nausea, and photosensitivity. Transient nausea and occasional vomiting have been observed following oral administration of high doses of 5-ALA. The incidence of nausea

following 30 mg/kg and 60 mg/kg (oral) was 7 and 15%, respectively. No vomiting was observed with the lower dose, while 8% of the patients vomited following the higher dose. In all instances, the nausea was mild and short lived (less than15 min.). When vomiting occurred, it was mild and occurred only once in each patient. The nausea or vomiting occurred within 2.5 to 3 hours after receiving the drug which did not interfere with the gut absorption of 5-ALA that occurs within 1 hour of oral ingestion.

Abnormalities in liver function have been observed in patients following ingestion of 5-ALA.

Webber et al. observed that almost one-quarter of all patients who received 5-ALA had at least one abnormality in liver function tests. More patients receiving low doses (< 30 mg/kg) developed abnormalities than those receiving high doses. Significant variations in the time of appearance of the abnormalities were also noted (12 to 120 hr. postoperatively). In all cases, liver function tests returned to normal within 2 months after receiving 5-ALA.

In a single-arm European study including 21 healthy male volunteers, erythema of the skin was provoked by direct exposure to ultraviolet light up to 24 hours after oral application of 5-ALA HCI (20 mg/kg/ body weight). PPIX photosensitization manifests as an unpleasant pricking, itching, or burning sensation under the skin after exposure to the sun. A systemic load above 10 mg/kg is required to develop skin photosensitization which lasts from approximately 24 to 48 hours following 5-ALA administration. It is for this reason that patients will be kept in subdued light conditions for up to 48 hours following surgery.

Possible drug-related mild nausea was reported in 1 of 21 volunteers. In another single-center study, 21 patients with malignant glioma received 0.2, 2, or 20 mg/kg body weight 5-ALA HCl followed by fluorescence-guided tumor resection. The only adverse reaction reported in this trial was one case of mild skin erythema occurring in a patient treated with the highest dose.

In a single-arm European study including 36 patients with malignant glioma, drug-related adverse events were reported in 4 patients (one patient: mild diarrhea, one patient: moderate hypesthesia, one patient: moderate chills, and one patient: arterial hypotension) 30 minutes after dosing with 5-ALA HCl20 mg/kg body weight prior to fluorescence-guided resection. Follow-up time was 28 days.

In a comparative, unblinded phase-III European trial (MC-ALS.3/GLI), 201 patients with malignant gliomas received 5-ALA HCI (20 mg/kg body weight). 176 of these underwent fluorescence-guided resection with subsequent radiotherapy. 173 patients received standard resection (without 5-ALA administration) and subsequent radiotherapy. With a follow-up of at least 180 days after administration, 2/201 (1.0 %) drug recipients experienced side effects (mild vomiting 48 hours after surgery and mild photosensitivity 48 hours after study surgery). A patient accidentally received an overdose of the medicinal product (3000 mg instead of 1580 mg) which was well tolerated. Respiratory insufficiency resolved completely with ventilation. A more pronounced asymptomatic transient increase of liver enzymes was observed in 5-ALA HCI recipients, peaking between 7 and 14 days. Increased levels of amylase, total bilirubin, and leukocytes, but decreased levels of platelets and erythrocytes were observed, but differences between treatment groups were not statistically significant.

Liver toxicity (from phase III European trial) as elevated liver function tests (LFTs) occurred in over 10% of patients after oral 5-ALA, anesthesia, and fluorescence-guided tumor resection. LFT changes included increased alanine aminotransferase (ALT), aspartate aminotransferase (AST), gamma glutamyltransferase (GGT) and blood amylase at 24 h, 7 d, and 6 weeks after 5- ALA ingestion. Approximately, 10% had Grade 3 or 4 elevations in GGT at 7 days; 5% had Grade 3 or 4 elevations in GGT at 6 weeks, and 1% had persistent ALT or AST at 6 weeks. **LFTs returned to normal in all patients.** In both groups of patients from the European phase III trial, (5-ALA and placebo control), 1 patient developed a hepatic serious adverse event (SAE). The 5-ALA patient developed cholelithiasis.

2.0 STUDY OBJECTIVES

2.1 Primary Objectives

2.1.1 To assess the feasibility of using oral Gleolan® as an adjunct diagnostic imaging tool for malignant tumor tissue fluorescence in a pilot cohort of head and neck and skull base cancer patients.

2.2 Secondary Objectives

- 2.2.1 To further characterize the diagnostic performance of Gleolan ® (5-ALA)-induced PPIX tissue fluorescence for detecting malignant tumor histopathology in head and neck and skull base cancers.
- 2.2.2. To determine the predictive values of individual Gleolan® fluorescence scores on detecting malignant tumor histopathology in head and neck and skull base cancers.

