2.3 Endpoints

2.3.1 Definition:

Safety: Gleolan®-related adverse events will be recorded using standardized toxicity criteria and known side effect profile up to 6 weeks after surgery. Monitoring for adverse events will take place before and after Gleolan® administration, 48h after surgery, 2 weeks and 6 weeks postoperatively.

2.3.1 Primary endpoint:

The feasibility of using oral Gleolan® as an adjunct diagnostic imaging tool for malignant tumor tissue fluorescence will be primarily assessed by computing sensitivity of intraoperative Gleolan® induced PPIX tissue fluorescence.

PPIX tissue fluorescence will be defined categorically as "no" (score 0), "low" (score 1), "medium" (score 2), and "high" (score 3) by operative surgeon, and images will be recorded. For purposes of computing measures of diagnostic performance a score of 0 will be considered a negative test result and a score of 1, 2 or 3 will be considered a positive test result.

2.3.2 Secondary endpoints:

2.3.2.1 The diagnostic performance of Gleolan® will further be assessed by computing measures of specificity, positive predictive value (PPV), negative predictive value (NPV), and accuracy of intraoperative Gleolan® induced fluorescence with a score of 0 will be considered a negative test result and a score of 1, 2 or 3 will be considered a positive test result.

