The definition of a positive test is the fluorescence score equal to or greater than 1 while a negative test is considered a score of 0. For the assessment of sensitivity and specificity, histological diagnoses of any upper aerodigestive head and neck cancer in addition to squamous cell carcinoma, carcinoma in situ, and severe and moderate dysplasia were classified as malignant, whereas light dysplasia and normal tissue will be classified as benign by pathologists. The analysis population includes all patients who sign the inform consent regardless of taking 5-ALA or not. Each patient is expected to contribute multiple samples and the pathologists will determine presence of malignancy in each sample. A contiguous table (fluorescence scores vs. pathological results) that presents the frequency and percentage of each cell will be prepared. A generalized estimating equation (GEE) model accounting for repeated measure within each patient will be used to estimate the sensitivity and specificity. For sensitivity and specificity, the dependent variable is the PPIX fluorescence test result (positive vs. negative) and the independent variable is presence of tumor cells (tumor vs. normal).

For PPV and NPV, a generalized estimating equation (GEE) model accounting for repeated measure within each patient will be used. The dependent variable is presence of tumor, and the independent variable is the test result. The point estimate along with a corresponding two-sided 95% confidence interval will be provided using PROC GENMOD.

The 5-ALA related adverse events will be recorded using standardized toxicity criteria and known side effect profile. Frequency of each observed adverse event will be calculated at each monitor time point. The rate of each adverse effect will be estimated as the number of adverse events within 6 weeks after surgery divided by the number of person days followed. The point estimate of the incidence rate along with a corresponding two-sided 95% confidence interval will be provided using PROC GENMOD. 46

The analyses will be conducted using SAS 9.4 software. Copyright ©[2002-2012] SAS Institute Inc.

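### Objective 2.2.2 asks for predictive values score by score, but scores 1, 2 and 3 get only descriptive counts, with no confidence interval and no allowance for repeated samples per patient

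*Combined protocol and SAP*

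**What the plan says.** Section 2.2 lists two secondary objectives. Objective 2.2.1 concerns overall diagnostic performance. Objective 2.2.2 is separate: "To determine the predictive values of individual Gleolan® fluorescence scores" for malignant histopathology.

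Section 2.3 has the surgeon grade fluorescence on four levels, 0 to 3. It then fixes, for the measures of diagnostic performance, that "a score of 1, 2 or 3 will be considered a positive test result". Endpoint 2.3.2.1 (specificity, PPV, NPV, accuracy) repeats that cut. The only other secondary endpoint, 2.3.2.2, is adverse events.

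Section 8.3 uses the same cut, a positive test being a "fluorescence score equal to or greater than 1 while a negative test is considered a score of 0". On predictive values it states: "For PPV and NPV, a generalized estimating equation (GEE) model accounting for repeated measure within each patient will be used". It continues: "The dependent variable is presence of tumor, and the independent variable is the test result". A two-sided 95% interval is promised for that model. The Study Summary describes the same analysis.

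Section 8.3 also plans a cross-table of fluorescence scores against pathology, with cell frequencies and percentages. Section 5.2.2 plans predictive values by tumor type and histopathology, but not by score.

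**The concern.** The objective names individual scores, and the model that carries its key word, predictive value, sees only two categories. Objective 2.2.1 is already served by the binary PPV and NPV, so 2.2.2 adds something only if the scores are kept apart. No listed endpoint does that, and no planned model takes the four-level score as a covariate.

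What is at stake is whether the pilot can say, with stated uncertainty, how far a faint signal (score 1) and a strong one (score 3) differ in what they predict. Every other diagnostic estimate in section 8.3 that gets a model allows for several samples from one patient. The by-score result is left without that allowance and without an interval. If the method is chosen only after the scores and pathology are known, it becomes a post hoc choice.

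**Working it through.** **1. The plan's own sizing figure.** Section 8.2 takes sensitivity 0.85, prevalence 0.75 and a 95% interval no wider than 0.35, by the asymptotic method with continuity correction. The half-width is 1.96·√(p(1−p)/n₁) + 1/(2n₁), with the upper limit cut at 1.
- n₁ = 17 tumor samples: half-width 0.170 + 0.029 = 0.199, lower limit 0.651, width 1 − 0.651 = 0.349. N = 17/0.75 = 22.7, so 23. This matches.
- At 50% prevalence, n₁ = 11: half-width 0.211 + 0.045 = 0.256, width 0.406. This matches the stated 40.6%.

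Both figures concern sensitivity. The plan gives no precision for any predictive value.

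**2. Expected samples.** Section 8.2 expects three tumor samples and one normal sample from each of 23 patients: 69 + 23 = 92. It assumes sensitivity 85%, and quotes specificity of 53% to 96% from a glioma review.
- True positives: 0.85 × 69 = 58.65.
- False positives: 0.47 × 23 = 10.81 at specificity 53%; 0.04 × 23 = 0.92 at 96%.
- Positive samples: 69.5 or 59.6. Pooled PPV: 58.65/69.46 = 0.844, or 58.65/59.57 = 0.985.
- Score-0 samples: 10.35 + 12.19 = 22.5, or 10.35 + 22.08 = 32.4.

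**3. What the plan delivers for each score.**
- Score 0: NPV is P(benign | score 0), so P(malignant | score 0) = 1 − NPV. It has a GEE estimate and a 95% interval.
- Scores 1, 2 and 3: counts from the cross-table. A crude proportion can be formed, but row percentages are not specified, there is no interval, and the repeated samples are not accounted for.

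**4. What the pooled PPV cannot show.** Take specificity 53%, so 58.65 true and 10.81 false positives. The documents give no split across scores 1, 2 and 3. Three assumed splits:

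| Tumor share (1/2/3) | Normal share (1/2/3) | PPV by score (1/2/3) | Pooled |
|---|---|---|---|
| ⅓ / ⅓ / ⅓ | ⅓ / ⅓ / ⅓ | 0.844 / 0.844 / 0.844 | 0.844 |
| ⅓ / ⅓ / ⅓ | 0.6 / 0.3 / 0.1 | 0.75 / 0.86 / 0.95 | 0.844 |
| 0.20 / 0.35 / 0.45 | 0.7 / 0.2 / 0.1 | 0.61 / 0.91 / 0.96 | 0.844 |

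For example, score 1 in the last row: 0.20 × 58.65 = 11.73, 0.7 × 10.81 = 7.57, and 11.73/19.30 = 0.61. The binary model returns the same PPV in all three rows.

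**5. Precision if the scores are separated.** The Wilson width is 2z·√(p(1−p)/n + z²/(4n²)) / (1 + z²/n), with z = 1.96 and p set to the pooled PPV.
- Pooled PPV: 0.17 (n = 69.5, p = 0.844) or 0.08 (n = 59.6, p = 0.985).
- Assumed even split, n = 23.2 or 19.9 per score: 0.29 or 0.19.
- A score holding an assumed 10% of positives, n = 6.9 or 6.0: 0.50 or 0.41.

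These are before inflation for clustering. The within-patient correlation is not in the documents. To show its effect on the pooled PPV at specificity 53%: m = 69.46/23 = 3.02 positives per patient, and the design effect 1 + (m − 1)ρ is 1.61 at an assumed ρ = 0.3 and 2.01 at ρ = 0.5. The width rises from 0.17 to 0.215 and 0.239. By score, the inflation depends on how often samples from one patient share a score, which is unknown.

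**6. Dependence on the sampling ratio.** Hold sensitivity at 0.85 and specificity at 0.53. At the planned 75% tumor share the PPV is 0.844. At 50%, the alternative named in section 8.2, it is 0.85/(0.85 + 0.47) = 0.644. By-score values depend on the ratio in the same way.

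**The case against.** The strongest reply is that the cross-table already answers the objective at the level a pilot needs. Its counts give P(malignant | score) by division. The resulting proportion is a legitimate point estimate, since it equals the GEE estimate under an independence working correlation. Score 0 is fully covered through the NPV. With 23 patients, intervals for single scores would be wide and might overlap, so a descriptive table is defensible.

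Much of this stands. A reader might infer that objective 2.2.2 gets no valid estimate or interval at all. The documents do not support that, because of the NPV interval and the table. A reader might also infer that the plan conceals any gradient across scores, or that the pooled PPV overstates a faint signal. Neither follows: the counts that would reveal a gradient are to be tabulated, and section 8.2 says where samples are taken, not how bright they are. A flat pattern across scores fits the plan's figures equally well.

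The reply does not supply an endpoint for 2.2.2, an interval for scores 1 to 3, or any allowance for repeated samples. Low precision is a reason to show the interval, not to omit it.

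A fair point also applies to the remedy. If a score has no benign samples, a logit model has no finite estimate at that level, and an exact interval that counts samples would ignore the clustering. The fix has to deal with both.

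**Conclusion.** The concern holds in a limited form. Objective 2.2.2 has no matching endpoint. Of the four scores, one has a clustered estimate with an interval, and three have only counts and percentages. The planned PPV cannot distinguish equal by-score values from a range of 0.61 to 0.96.

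That range is an illustration. It rests on the plan's 3:1 sampling, its 85% sensitivity, the low end of its quoted specificity range, and splits across scores that are assumed. The gap in the plan rests on none of these; it follows from sections 2.2, 2.3 and 8.3 read together. The point is minor, because it affects a secondary objective of a pilot and leaves the primary sensitivity analysis untouched. It is worth settling before the data are examined.

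**What to change.** Add an endpoint to section 2.3.2: P(malignant | score) for each of scores 0, 1, 2 and 3. In section 8.3, refit the planned PPV model with score as a four-level class variable in place of the binary test result, using an independence working correlation and robust variance. Report each probability with its patient-clustered 95% interval, beside the result for 0 versus 1 or more.

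Where a score has only malignant or only benign samples, take that level out of the model and give an exact interval based on the number of contributing patients, not samples. If all samples at a score are malignant and k patients contribute, the two-sided 95% lower limit is 0.025^(1/k): 0.54 for an assumed k = 6, and 0.85 if all 23 contribute.

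State in the plan that the values reflect the 3:1 tumor-to-normal sampling, and that the intervals will be wide, with the widths shown above.

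The cost is one extra model and one table. No new data are needed, since section 8.2 already has each region marked with its score. The downside is imprecise estimates for sparse scores.
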